### 3.4 Number of Subjects

A maximum of 40 evaluable patients will be enrolled in the study using a Simon's two-stage design for the primary endpoint. Patients who are enrolled at the maximally tolerated dose of

nivolumab during the run-in phase will be included in the determination of the primary endpoint. Non-evaluable patients will be replaced per the replacement policy (see section 8.2.5). For the primary endpoint, this design yields a type I error rate of 0.05 and power of 80% if the true rate of completion of adjuvant therapy is 0.7.

### 3.5 Eligibility Criteria

Patients must have baseline evaluations performed prior to the first dose of study drug and must meet all inclusion and exclusion criteria. In addition, the patient must be thoroughly informed about all aspects of the study, including the study visit schedule and required evaluations and all regulatory requirements for informed consent. The written informed consent must be obtained from the patient prior to enrollment. The following criteria apply to all patients and all eligibility criteria must be met prior to enrollment on the study unless otherwise specified.

#### 3.5.1 Inclusion Criteria

1. Males and females  $\geq 18$  years of age.
2. Histologically or cytologically confirmed nasopharyngeal carcinoma, stage II-IV by AJCC 7th edition, endemic-type (defined as WHO type 2a and 2b nonkeratinizing or undifferentiated subtypes, excluding WHO type I keratinizing subtype) performed on a biopsy that occurred within 90 days of registration.
3. PET-CT (preferred) or a CT of chest, abdomen, and pelvis within 60 days of registration showing radiographic stage II to IVB nasopharyngeal cancer.
4. No distant metastasis as verified by one of the study investigators.
5. Documentation that the patient is a candidate for chemoradiation of their nasopharyngeal cancer by one of the study investigators.
6. Ability to tolerate radiation therapy (e.g. lie flat and hold position for treatment).
7. Measurable disease as defined by RECIST v1.1.
8. ECOG performance status of 0 to 1.
9. Lack of contraindications to systemic immunotherapy (see list of exclusions below).
10. Resolution of all acute toxic effects of any prior chemotherapy, radiotherapy or surgical procedures to NCI CTCAE Version 5.0 grade 1.
11. Adequate hepatic, hematologic, and renal indices permitting administration of cisplatin and nivolumab (within 14 days of registration):

Hepatic Function:

Aspartate aminotransferase (AST) and alanine aminotransferase (ALT)  $\leq 3 \times$  upper limit of normal (ULN);

Total bilirubin  $\leq 1.5 \times$  ULN (except subjects with Gilbert Syndrome, who can have total bilirubin  $< 3.0$  mg/dL)

Adequate bone marrow function:

WBC  $\geq 2000/\mu\text{L}$

Neutrophils  $\geq 1500/\mu\text{L}$

Platelet  $\geq 100 \times 10^3/\mu\text{L}$

Hemoglobin  $> 9.0$  g/dL

Adequate renal function:

Serum creatinine  $\leq 1.5 \times$  upper limit of normal (ULN)

OR

Creatinine clearance  $> 40 \text{ mL/min}$  (or  $\geq 50 \text{ mL/min}$  for Singapore sites only) (if using the Cockcroft-Gault formula below):

$$\text{Female CrCl} = (140 - \text{age in years}) \times \text{weight in kg} \times 0.85$$

$$72 \times \text{serum creatinine in mg/dL}$$

$$\text{Male CrCl} = (140 - \text{age in years}) \times \text{weight in kg} \times 1.00$$

$$72 \times \text{serum creatinine in mg/dL}$$

12. Women of childbearing potential must have a negative serum pregnancy test within 24 hours prior to the first dose of study treatment and agree to use appropriate highly effective methods of contraception, during the study and for 5 months following completion of study treatment;

A "Woman of childbearing potential" is defined as any female who has experienced menarche and who has not undergone surgical sterilization (hysterectomy or bilateral oophorectomy) or who is not postmenopausal. Menopause is defined clinically as 12 months of amenorrhea in a woman over 45 in the absence of other biological or physiological causes. In addition, women under the age of 62 must have a documented serum follicle stimulating hormone (FSH) level less than 40 mIU/mL.

Female Subjects:

Women of child bearing potential are expected to use one of the highly effective methods of contraception listed below.

Male Subjects:

Male subjects must inform their female partners who are women of child bearing potential of the contraceptive requirements and are expected to adhere to using contraception with their partner. Female partners of male subjects, who are women of child bearing potential, are expected to use one of the highly effective

methods of contraception listed below. In addition, male subjects are expected to use a condom as noted in the list below.

Highly Effective	Progestogen only hormonal contraception associated with inhibition of ovulation
	Hormonal methods of contraception including oral contraceptive pills (combination of estrogen and progesterone), vaginal ring, injectables, implants and intrauterine devices (IUDs)
	Non-hormonal IUDs such as ParaGard®
	Bilateral tubal ligation
	Vasectomized Partner
	Intrauterine hormone-releasing system (IUS)
	Complete abstinence
Other Methods	Condom
Unacceptable Methods	Vaginal sponge
	Progestin only pills
	Cervical cap with spermicide
	Periodic abstinence (calendar, symptothermal, post-ovulation methods)
	Withdrawal (coitus interruptus)
	Spermicide only
	Lactation amenorrhea method (LAM)
A male and a female condom must not be used together	

13. Men with a female partner of childbearing potential must agree to use highly effective methods of contraception or any contraceptive method with a failure rate of less than 1% per year during the study and for 7 months following completion of study treatment.
14. Ability to sign informed consent.

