#### Cisplatin Dose Modifications for Non-Hematologic Adverse Events during Concurrent Radiation

**Neutropenic Fever:** If on the day of scheduled treatment with cisplatin the absolute neutrophil count (ANC) is  $< 1200$ , hold treatment until ANC  $\geq 1200$ , then treat at 100% dose. Neutropenic fever will require permanent 25% dose reduction. Febrile neutropenia is fever of unknown origin without clinically or microbiologically documented infection; ANC  $< 1.0 \times 10^9 \text{ L}$ , fever  $> 38.5^\circ\text{C}$ .

**Thrombocytopenia:** If on the day of scheduled treatment with cisplatin the platelet count is  $< 75,000$ , hold treatment until platelets are  $> 75,000$ , then treat at 100% dose. Thrombocytopenia that results in bleeding will require a 25% dose reduction.

**Renal Adverse Events:** Cisplatin should be administered on the scheduled day of treatment using the following guidelines:

**Note:** If creatinine is > 1.2 mg/dl, clearance must be done in order to make dose adjustment. If the calculated nomogram is 50 mL/min or above, a 24-hour urine collection is not needed, but if the nomogram calculation is less than 50 mL/min, a 24-hour urine collection is mandated.

Once the creatinine has met the above parameters, cisplatin may be restarted with the modifications below, based on the creatinine at the time the cisplatin was held: In general, cisplatin should be held for weekly intervals (rather than restarting cisplatin later in the same week that a dose limiting AE is seen).

Cisplatin dose modifications for creatinine during concurrent radiation			
Creatinine (mg/dL)		Creatinine clearance, measured or calculated ml/min	Cisplatin dose reduction
≤ 1.2	or	> 50	100%
> 1.2	and	40-50	50%
		< 40	Discontinue drug

**Neurologic (neuropathy) adverse events:** If any signs of grade 3 or greater neurotoxicity occur, discontinue cisplatin.

Grade (CTCAE v5.0)	Dose Reduction
0-1	None
2	One dose level
3-4	Discontinue drug

**Ototoxicity:** For new clinical hearing loss not requiring a hearing aid or for tinnitus that interferes with activities of daily living, treat at 50% dose reduction. For hearing loss requiring a hearing aid, discontinue cisplatin. Continue radiation. If the physician is unsure about the severity of the hearing loss, an audiogram is encouraged.

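### Criterion 11's creatinine-only route can admit a patient whose clearance would stop cisplatin under the protocol's own renal rule (minor inconsistency)

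*Combined protocol and SAP*

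**What the plan says.** Section 3.5.1, criterion 11, sets the purpose of the laboratory limits: "Adequate hepatic, hematologic, and renal indices permitting administration of cisplatin and nivolumab (within 14 days of registration". The renal limits are serum creatinine no higher than 1.5 x ULN, the word OR, and then creatinine clearance above 40 mL/min. The clearance limit carries a stricter value of 50 mL/min "for Singapore sites only) (if using the Cockcroft-Gault formula below". Criterion 5 separately asks for "Documentation that the patient is a candidate for chemoradiation of their nasopharyngeal cancer by one of the study investigators".

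Section 5.2.2, under non-hematologic adverse events during concurrent radiation, opens its renal rule with "Cisplatin should be administered on the scheduled day of treatment using the following guidelines". It continues: "If creatinine is > 1.2 mg/dl, clearance must be done in order to make dose adjustment", and "if the nomogram calculation is less than 50 mL/min, a 24-hour urine collection is mandated". Its table gives:

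- full dose if creatinine is at most 1.2 mg/dL or clearance is above 50 mL/min;
- a 50% entry if creatinine is above 1.2 and clearance is 40 to 50;
- stop the drug if clearance is below 40.

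The clearance column is headed "Creatinine clearance, measured or calculated ml/min".

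The screening list in section 6.1.1.1 includes weight and serum creatinine, but neither a clearance nor a 24-hour urine. In Dose Schedule 1 (section 3.2), nivolumab is given 14 days before the first cisplatin dose. Section 8.2.5 counts anyone who has received any study drug as evaluable and allows replacement only for drop-out before nivolumab.

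**The concern.** Criterion 11 is meant to confirm that the kidneys can take cisplatin, but it uses a different test from the one that later governs cisplatin. A patient who satisfies the creatinine limit never reaches the clearance limit, so the 40 mL/min floor does not apply to that patient, and neither does the Singapore 50 mL/min floor. The same renal function can then be adequate for entry and too poor for cisplatin.

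What is at stake is modest but avoidable. In Dose Schedule 1 a patient enrolled for a cisplatin-based curative regimen could receive a priming dose of study drug and take one of at most 40 evaluable places. Only then would the protocol's own rule stop the cisplatin. The information needed to foresee this is available at screening.

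**Working it through.** The plan states no figure to reproduce here. The check compares two rules and asks whether a patient can fall between them.

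**Inputs.** The limits are those of criterion 11 and the section 5.2.2 table. The clearance formula is Cockcroft-Gault as printed in section 3.5.1: (140 − age) × weight × k / (72 × creatinine), with k = 1 for men and 0.85 for women. ULN for creatinine is not in the documents, so a range is assumed. The patients are illustrative.

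**Step 1: when the gap exists.** The creatinine route reaches above 1.2 mg/dL only if 1.5 × ULN > 1.2, that is, ULN > 1.2/1.5 = 0.8 mg/dL.

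| Assumed ULN (mg/dL) | 0.8 | 0.9 | 1.0 | 1.1 | 1.2 | 1.3 |
|---|---|---|---|---|---|---|
| Highest creatinine admitted at any clearance (1.5 × ULN) | 1.20 | 1.35 | 1.50 | 1.65 | 1.80 | 1.95 |

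At 0.8 there is no gap. At each higher value shown there is one.

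**Step 2: whether such patients can have clearance below 40.** The smallest ULN that admits a patient on creatinine is creatinine/1.5.

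| Patient | Creatinine | Calculated clearance (mL/min) | ULN needed |
|---|---|---|---|
| Man, 65 y, 60 kg | 1.7 | 75 × 60 / (72 × 1.7) = 36.8 | 1.14 |
| Woman, 60 y, 50 kg | 1.5 | 80 × 50 × 0.85 / (72 × 1.5) = 31.5 | 1.00 |
| Same woman | 1.3 | 80 × 50 × 0.85 / (72 × 1.3) = 36.3 | 0.87 |

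Each passes the creatinine limit, fails the clearance limit, and has a calculated value in the stop range. The gap depends on age, weight and sex: a man of 45 y and 65 kg with creatinine 1.8 has 95 × 65 / (72 × 1.8) = 47.6 and is not in that range.

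**Step 3: what measurement could change.** Section 5.2.2 requires a 24-hour urine when the calculated value is under 50, so a low calculated value does not by itself place a patient in the stop row. To pass 40, the measured value would have to exceed the calculated one by 40/36.76 − 1 = 8.8%, 40/31.48 − 1 = 27.1% and 40/36.32 − 1 = 10.1% respectively.

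**Step 4: the Singapore limit.** A man of 65 y and 60 kg with creatinine 1.3 has 75 × 60 / (72 × 1.3) = 48.1. This is under 50, yet he is eligible at a Singapore site on creatinine alone if ULN is at least 0.87.

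**Step 5: whether the cisplatin rule reaches the first dose.** The renal rule is framed around the scheduled treatment day, and section 5.2.2 bases dose changes on laboratory values from the 24 hours before cisplatin. Neither exempts dose 1.

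**Step 6: timing.** The Day 1 eligibility check in section 6.1.1 repeats the same criteria, so it does not expose the gap. In Dose Schedule 1 the clearance that section 5.2.2 requires comes 14 days after nivolumab has begun. Dose Schedules 2 and 3 have no priming dose.

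**The case against.** The strongest objection is that section 5.2.2 is not an entry rule. It sits under adverse events during radiation, an instruction to stop a drug suggests the drug has been started, and part of the lead-in concerns resumption: "cisplatin may be restarted with the modifications below, based on the creatinine at the time the cisplatin was held". This stands to the extent that a first-dose bar is the better reading, not an explicit rule.

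Second, the creatinine cell of the below-40 row is blank in the text as extracted. Reading it as above 1.2 mg/dL is an inference from the full-dose row and the note on when a clearance is needed. Under that inference a woman of 70 y and 45 kg with creatinine 1.1 and clearance 70 × 45 × 0.85 / (72 × 1.1) = 33.8 gets full dose. If the row applies at any creatinine, she is in conflict too.

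Third, the investigator has prompts: the wording of criterion 11, criterion 5, and the freedom in section 5.1.1.2 to follow institutional practice and local administration guidelines. Age, weight and creatinine are all to hand, so an alert investigator may catch the case. But none of these supplies a renal number. The carboplatin switch in section 5.5.1 is worded for toxicity caused by cisplatin, not for baseline impairment.

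Fourth, eligibility limits and on-treatment dose limits need not be identical. That is true in general, but this criterion says it exists to permit cisplatin.

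A reader might infer that such a patient is lost to the primary endpoint, or that the completion rate or the two-stage design is biased. The documents do not support this. The table stops cisplatin, not protocol therapy, and section 8.4.2 counts post-chemoradiation nivolumab cycles, so the patient can still be a completer.

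**Conclusion.** The inconsistency is real but minor. With ULN above 0.8 mg/dL, criterion 11 can admit a patient with creatinine above 1.2 mg/dL and clearance below 40 mL/min, for whom section 5.2.2, on its better reading, would stop cisplatin. For patients who pass on creatinine, the Singapore limit has no effect.

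The conclusion rests on three assumptions: the ULN, application of the renal rule from the first dose, and the inferred creatinine condition in the below-40 row. The documents give no frequency. Several conditions must coincide, so the number affected is probably small. The harm is an avoidable priming dose and a place that cannot be refilled, in Dose Schedule 1 only. Type I error, power and sample size are unchanged.

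A reader might also conclude that every patient needs a clearance floor, by changing OR to AND. That does not follow: it would exclude patients such as the woman with creatinine 1.1 and clearance 33.8, to whom section 5.2.2, as read here, gives full dose.

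**What to change.** Reword the renal part of criterion 11 to: *Serum creatinine ≤1.5 x ULN and ≤1.2 mg/dL; OR creatinine clearance, measured or calculated, >40 mL/min (≥50 mL/min at Singapore sites).* When creatinine is above 1.2 mg/dL, calculate Cockcroft-Gault at screening from the age, weight and creatinine already available. A 24-hour urine before C1D1 should be optional, for example to rescue a patient with a low calculated value. It should not become a new mandatory screening procedure. State which value decides if both exist.

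The cost is a wording amendment and a hand calculation. A few patients with creatinine above 1.2 mg/dL and clearance of 40 or less (below 50 in Singapore) become ineligible. Nobody with creatinine at or below 1.2 loses eligibility, and a man of 45 y and 90 kg with creatinine 2.0 stays eligible at 95 × 90 / (72 × 2.0) = 59.4. Accepting measured values could also admit a patient above 1.5 x ULN whose calculated value is 40 or less but whose measured value is higher.

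Three things remain uncovered:

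- A patient admitted on a calculated 40 to 50 could still measure below 40 later. For a man of 65 y and 60 kg with creatinine 1.5, the calculated value is 75 × 60 / (72 × 1.5) = 41.7, and a measurement more than 1 − 40/41.67 = 4% lower would do it.
- Renal decline after screening is not addressed.
- If the below-40 row is meant to apply at any creatinine, the rewording does not reach patients at 1.2 mg/dL or less. The sponsor should make that cell explicit.

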In a 3-month toxicity study, twice weekly IV doses of nivolumab were administered to 6 animals per sex at doses of 0, 10, and 50 mg/kg and were well tolerated; no clinical signs of toxicity or drug-related body weight, cardiovascular, neurologic, respiratory, urinalysis, hematologic, organ weights, or macroscopic or histologic pathology findings were observed. Serum chemistry changes were limited to a reversible 28% decrease in T3 at Week 13 in females treated with 50 mg/kg. T4 and TSH levels were not affected, and in males treated with 50 mg/kg, no changes in T3, T4, or TSH levels were observed. Although anti-nivolumab antibodies were only detected in 1 of 24 animals, it is possible that high nivolumab concentrations interfered with the assay. The results of this study showed that nivolumab was well tolerated when administered by IV injections twice weekly for 3 months at doses up to 50 mg/kg (5 $\times$  the clinical dose of 10 mg/kg), with no adverse effects on any of the evaluated parameters. In addition, an enhanced pre- and postnatal development (ePPND) study in pregnant cynomolgus monkeys with nivolumab was conducted.

Administration of nivolumab at up to 50 mg/kg 2QW was well tolerated by pregnant monkeys; however, nivolumab was determined to be a selective developmental toxicant when administered from the period of organogenesis to parturition at 10 mg/kg (area under the concentration-time curve [AUC] from time zero to 168 hours [AUC(0-168 h)] 117,000 ug $\cdot$ h/mL). Specifically, increased developmental mortality (including late gestational fetal losses and extreme prematurity with associated neonatal mortality) was noted in the absence of overt maternal toxicity. There were no nivolumab-related changes in surviving infants tested throughout the 6-month postnatal period. Although the cause of these pregnancy failures was undetermined, nivolumab-related effects on pregnancy maintenance are consistent with the established role of PD-L1 in maintaining fetomaternal tolerance in mice.

No mass balance or metabolism studies with nivolumab have been conducted in animals. The expected in vivo degradation of monoclonal antibodies is to small peptides and

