##### 6.1.1.1 Screening Assessments

Patients will undergo screening assessments within 30 days before receiving the first dose of nivolumab, unless otherwise noted. Study procedure-related AEs that occur after signing of the

Informed Consent Form (ICF) and before administration of nivolumab will also be collected.

The Screening procedures and assessments must be completed within 30 days prior to the Cycle 1 Day 1 Visit, unless otherwise noted.

- Physical examination
- Weight
- Vital signs
- Complete medical history
- Baseline conditions assessment
- Disease Assessment
- ECOG Performance status
- History of prior treatments and any residual toxicity relating to prior treatment
- Concomitant medications and procedures
- Biopsy or archived tissue procurement
  - Archived tissue: If no intervening treatment received, adequate tissue available, and performed within 90 days of day 1 (cycle 1 day 1) of study treatment; otherwise, fresh biopsy required. See Appendix 4.
- Complete blood count (CBC) with differential and platelet count (within 14 days of Cycle 1 Day 1)
- Serum chemistry assessment (within 14 days of Cycle 1 Day 1), including:
  - Alkaline phosphatase, aspartate aminotransferase/alanine aminotransferase (ALT/AST), total bilirubin, total protein, albumin, calcium, phosphorus, magnesium, blood urea nitrogen (BUN), creatinine, glucose (fasting), potassium, sodium, chloride, bicarbonate, uric acid, LDH, fasting lipid panel (LDL, total cholesterol, triglycerides).
- Serum or urine pregnancy test within 7 days prior to the start of study drug in pre-menopausal females.
- TSH evaluation (within 14 days of Cycle 1 Day 1)
- Urinalysis (within 14 days of Cycle 1 Day 1)
- MRI of nasopharynx, face, and neck within 60 days prior to start of study drug.
- Whole body PET-CT of top of head to mid-thigh (preferred) or CT of chest, abdomen, and pelvis within 60 days prior to the start of study drug.
- Research blood draw: collection of peripheral blood for EBV DNA and correlative biomarker studies.
- All blood draws may be done within 7 days prior to start of therapy unless otherwise specified.
- Contraceptive counseling
- Serum pregnancy test (by local laboratory) ≤ 1 days prior to the first day of dosing for women of childbearing potential. If the serum pregnancy test results are not available on C1D1, a urine pregnancy test can be performed on C1D1 to confirm that the patient is not pregnant prior to dosing.
- Baseline quality of life assessments

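### The FSH condition attached to the menopause definition in inclusion criterion 12 runs the wrong way and can misclassify amenorrheic women aged 46 to 61; the unsafe misclassification is probably rare.

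*Combined protocol and SAP*

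**What the plan says.** Criterion 12 in section 3.5.1 contains four linked statements.

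- The duty: "Women of childbearing potential must have a negative serum pregnancy test within 24 hours prior to the first dose of study treatment and agree" to highly effective contraception during the study and for 5 months afterwards.
- Who is of childbearing potential: a woman past menarche "who has not undergone surgical sterilization (hysterectomy or bilateral oophorectomy) or who is not postmenopausal".
- What menopause means: "Menopause is defined clinically as 12 months of amenorrhea in a woman over 45 in the absence of other biological or physiological causes".
- The FSH condition, which follows directly and is introduced as an addition: "women under the age of 62 must have a documented serum follicle stimulating hormone (FSH) level less than 40 mIU/mL".

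Section 6.1.1.1 sets two screening tests. One is "Serum or urine pregnancy test within 7 days prior to the start of study drug in pre-menopausal females". The other is "Serum pregnancy test (by local laboratory) ≤ 1 days prior to the first day of dosing for women of childbearing potential". Table 6.1, footnote o, repeats both, and the table schedules pregnancy testing at screening only. FSH is in neither the screening list nor Table 6.1, although criterion 12 requires a documented value.

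Exclusion 21 (section 3.5.2) bars women who are pregnant or breastfeeding, whatever their classification. Section 6.1.1.1 also lists contraceptive counselling without limiting it to any group.

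**The concern.** A laboratory value placed straight after a clinical definition of menopause, and introduced as an addition to it, reads as a confirmatory test. Such a test should pick out women whose ovarian function has ceased. Because FSH rises when that happens, a requirement for a value below a limit picks out the opposite group.

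The classification matters because every scheduled pregnancy test, and the contraception duty for women, depends on menopausal status or childbearing potential. No later scheduled test would catch a mistake. Section 1.2.2.1 reports that "nivolumab was determined to be a selective developmental toxicant when administered from the period of organogenesis to parturition", with increased developmental mortality. Section 7 requires permanent discontinuation of the product if pregnancy is discovered, and handling of pregnancy as a serious adverse event. The same definition decides which female partners of male participants are expected to use contraception.

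**Working it through.** The plan states no figure to reproduce. The check is logical, followed by a bound on the number of patients.

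**Premise.** FSH is high after ovarian function ceases. This is general physiology; the document gives no second FSH value or direction to compare with.

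**Step 1: who is affected.** The menopause definition needs age over 45 and a year of amenorrhea without another cause. The FSH condition applies under 62. The rule therefore acts on amenorrheic women aged 46 to 61. Women who are younger or still menstruating are not released by it.

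**Step 2: apply each reading to two illustrative women, neither sterilised, both amenorrheic for 12 months without another cause.** A is 48 with FSH 15 mIU/mL; B is 58 with FSH 80 mIU/mL.

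| Reading of criterion 12 | A (FSH 15) | B (FSH 80) |
|---|---|---|
| 1. FSH confirms menopause; childbearing potential means not sterilised *and* not postmenopausal | Classed as postmenopausal: no pregnancy test or contraception required | Menopause not confirmed: tests and contraception required |
| 2. FSH confirms menopause; *or* taken literally | Still of childbearing potential because not sterilised; 24-hour test and contraception apply. Not pre-menopausal, so outside the 7-day test | Of childbearing potential; 24-hour test and contraception apply. Menopause not confirmed, so treated as within the 7-day test |
| 3. FSH is a separate eligibility limit | Meets it | Excluded, since section 3.5 requires all criteria to be met |

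Reading 1 classifies both women in the wrong direction. Reading 2 makes the menopause clause almost idle: a woman would leave the childbearing-potential group only if she were both sterilised and postmenopausal. Even then, the 7-day test still turns on menopausal status. Reading 3 would keep out most postmenopausal women under 62, which nothing in the plan suggests is intended. No reading gives a sensible classification. Reading 1 is the evident intent, apart from the direction of the inequality.

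**Step 3: how many patients.** The document gives no sex or age mix. Assume that 25% to 35% of 40 patients are women and that one third of them are aged 46 to 61:

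- Women: 40 × 0.25 = 10 to 40 × 0.35 = 14.
- Aged 46 to 61: 10 / 3 = 3.3 to 14 / 3 = 4.7, so about 3 to 5.

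This counts all women of that age. The rule classifies only those with 12 months of amenorrhea, so 3 to 5 is a ceiling for errors in both directions together.

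The unsafe error also needs FSH below 40. Let *s* be the share of women aged 46 to 61 who are amenorrheic for a year and have FSH below 40. The expected number is 3.3*s* to 4.7*s*. It stays at or below one if *s* ≤ 1 / 3.3 = 0.30 at the low end, or *s* ≤ 1 / 4.7 = 0.21 at the high end. On the premise, most women amenorrheic for a year at this age would have high FSH, so *s* should be small and zero or one patient is plausible. The other affected women fall into the conservative error: testing and contraception that they do not need.

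**The case against.** The strongest objection is that the harm does not follow from the literal text. It needs the *or* in the childbearing-potential definition to be read as *and* while the inequality is left as printed. Taken literally, woman A keeps her 24-hour test and contraception duty. This stands as a limit on the claim: the release from both follows on the intended reading, not on every reading. It does not rescue the criterion, because the literal *or* defeats the purpose of having a menopause clause.

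Second, other protection remains. Exclusion 21 applies to any pregnant woman, and contraceptive counselling is unrestricted. This also stands. Neither replaces a mandatory test, but a reader who infers that all protection is removed goes further than the documents allow.

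Third, a reader might take 3 to 5 as the number of women wrongly released from testing. The documents do not support that: the figure rests on an assumed mix, ignores the amenorrhea condition, and combines an unsafe error with a more common conservative one.

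Fourth, this is a wording slip, and it leaves the primary endpoint, the two-stage boundaries, the dose-limiting toxicity rules and the analysis populations untouched. That is correct. The case for correction rests on participant safety and on sites in a multicenter trial applying the same rule.

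**Conclusion.** The concern holds. The FSH condition is wrong as written: reversed as a confirmation of menopause, and untenable as an eligibility limit. The conclusion depends on the premise about FSH and on the absence of any correcting text elsewhere in the document.

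The practical reach is small. Only amenorrheic women aged 46 to 61 are affected, at most about 3 to 5 of 40 in both directions under the assumed mix, with plausibly zero or one in the unsafe direction. A reader might infer that women with persisting ovarian function will generally escape pregnancy testing. The documents do not support that: the year of amenorrhea is still required, the release depends on how the *or* is read, and known pregnancy remains an exclusion. The reason to act is that a reproductive-safety criterion should not depend on each site noticing and overriding an error.

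**What to change.** The sponsor should amend the text in four places.

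1. Correct the direction of the FSH condition in criterion 12. No cut-off is proposed here.
2. State in the same sentence that FSH serves to confirm postmenopausal status and is not an eligibility limit.
3. Repair the *or* in the definition of childbearing potential so that the roles of sterilisation and menopause are unambiguous.
4. Reconcile criterion 12 with section 6.1.1.1 and with Table 6.1 and its footnote o. Use one classification for both pregnancy tests, and list the FSH test for the women to whom criterion 12 applies it.

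The cost is a short text amendment across these sections. Criterion 12 already requires the FSH result, so listing it adds no new test. Design, sample size and analysis are unaffected.
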